3.9 NON-MEDICAL CRIMINAL JUSTICE OCCURRENCES

The notifiable probation Incidents and Offences will be collected. These include death, attempted murder, murder, manslaughter, rape, grievous bodily harm and terrorism-related offence. As five of these items will be collected though Adverse Events or Serious Adverse Events, only two items will be captured as Nonmedical Criminal Justice Occurrences for male participants and their (ex)-partners. These items are Nonmedical Attempted Murder and Non-medical Terrorism-related offence.

In the event of non-medical attempted murder, the date of the first occurrence, the last occurrence and frequency will be collected. Examples of non-medical attempted murder include tampering with a partner or ex-partners brakes (car) and planning an arson attack/fire setting e.g. getting the materials together to set a fire at a domestic dwelling, with the intention of causing significant harm. In both cases the intended victim would not necessarily know and not suffer any direct physical or psychological damage.

In instances of non-medical terrorism-related offences, they will be classed under one of four categories following the definition of the Terrorism Act 2000. These categories are 1) Created a serious risk to the health or safety of the public or a section of the public, 2) Action designed seriously to interfere with or seriously to disrupt an electronic system 3) A threat is designed to influence the government or to intimidate the public or a section of the public and 4) A threat is made for the purpose of advancing a political, religious or ideological cause.

3.10 MEASURES TO PROMOTE PARTICIPANT RETENTION

Researchers will record participants and (ex)-partners contact details (mobile, WhatsApp, house phone, email) to maintain contact. To enhance retention, participants will be asked for the contact details of up to 3 family members or friends and of the services they attend (e.g. pharmacy, GP, alcohol and drug treatment service, social worker) in case the researchers cannot contact the participant using their contact details.

Researchers will keep in regular contact (monthly) with the participants and (ex)-partners to remind them about key timepoints in the study. They will be reminded of their interview dates by text and email. Consent to follow participants up through these contacts if it is not possible to contact them using their contact details will be sought. All personal data will be stored on SharePoint separate to the research data.

Addressing digital poverty and literacy

Participants will be provided with tablets with 5GB of mobile data to address digital poverty. Additional monthly mobile data throughout the duration of the study is contingent on ADVANCE-D engagement and attendance. If men prefer to use their own technology, they will be reimbursed for their data. If men do not attend any sessions each month (group or website), researchers will ask men to return the tablet and their monthly mobile data will not be topped-up. Participants will be asked to return their tablet to probation /JSW at the end of the study. These will be collected by the research team and reused at other sites where possible. Mobile data allowance will be used only for the purpose of taking part in the ADVANCE-D Programme.

The responsibility for returning the device rests with the participant. Participants' engagement with probation may be longer than the 14-week ADVANCE-D Programme. Participants will be expected to return the tablet to probation or someone acting for them if not possible. Participants will be prompted twice and offered/ sent a free return envelope to encourage return. If participants are arrested for further offending and/or returned to custody, they would be asked to make arrangements for a friend or support worker to return the device to probation or the ADVANCE-D team. If the device is not returned, it will be remotely wiped as far as is possible, remove website access for the participant and record their details as having been offered ADVANCE-D and not completed, for research and operational purposes. The rate of devices reported as lost/stolen/broken will be tracked.

To address digital literacy, participants will be provided with a written and video guide of how to use the tablet to participate in the ADVANCE-D Programme.

Reimbursement for time

Only (ex)-partners will receive a £20 voucher for their time for participating in the baseline interview (women) and follow-up research interviews post-intervention (up to £20 x 3 = £60). They will also receive £20 for participating in each brief semi-structured interview (up to £20 x 2 = £40).

4. Interventions

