3.7.10 PROCESS EVALUATION

Context, fidelity, dose delivered, dose received, reach and recruitment for ADVANCE-D will be evaluated.⁸⁵ Longitudinal qualitative interviews (at 4- and 12- months) with 40 men receiving ADVANCE-D and their (ex)-partners and with staff post intervention will provide in-depth understanding of mechanisms of action, how context affects implementation, engagement, and behaviour change.

The process evaluation will assess six priority areas:

1. Context – what are the local factors that influence intervention implementation

End of intervention focus groups/interviews will be conducted with the probation/JSW staff and women's support workers/ integrated support services that supported the intervention delivery to understand its implementation in practice and understand local context.

2. Fidelity – to what extent is the intervention delivered as conceived

All group sessions will be video recorded with consent. A random sample of 10% will be checked for fidelity. In addition, notes from integrity management meetings between the facilitators and the practitioners in the ADVANCE research team will contribute to these findings.

Co-applicants of the NIHR Programme grant that is funding the study, and that developed the intervention from King's College London, The University of Edinburgh, The University of Edinburgh, [name], Independent Consulting Psychologist (UK), and the University of Manchester will have access to the video recordings of the sessions to assess fidelity of the delivery of the intervention.

3. Dose delivered – what amount of the intervention were participants offered

The number of ADVANCE-D intervention sessions offered will be recorded for all male study participants. The number of ISS worker contacts offered will be provided, where consent has been given.

4. Dose received – attendance

Quantitative data on attendance and retention in the intervention group and TAU (number of sessions attended in group intervention and number of times participant has attended for TAU and duration of these contacts) and with women's support services for victims/ survivors (number of times the female participant has attended a session in person or by phone with the women's support worker or has had a follow-up call with the women's support worker and duration of these contacts) will be recorded and collated with participants' consent by the service providers and shared with the research team.

5. Acceptability and outcomes

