10.4 STATISTICAL METHODS FOR PRIMARY AND SECONDARY OUTCOMES

10.4.1 STATISTICAL METHODS FOR PRIMARY OUTCOME

We will analyse the primary outcome using multi-level linear regression model, including assessments at 4 and 12 months to assess the difference in ADVANCE-D and control at 12-months (primary assessment time-point). Participants and PDU/JSWT will be fit as random effects, and pre-specified fixed effects for participant age, baseline IPV severity, and baseline ABI total score, and region. The adjusted mean difference (aMD) in the Abusive Behavior Inventory (ABI) total score between those from ADVANCE-D with CJOM compared to Usual CJOM will be presented with the associated two-sided confidence intervals (95% CI) and p-value, and intraclass correlation coefficient (ICC). The analysis will use the ITT population that will include all participants who were followed up at either the 4- or 12-month time-point. Pattern missingness will explore the missing data. A CACE will be developed as a sensitivity analysis to the primary analysis. Sensitivity analyses will be used for modelling the different intercurrent events. An additional sensitivity analysis will use the partner IPV data.

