10.6 INTERNAL PILOT

INTERNAL PILOT: 168 participants from 12 clusters will be randomised in the internal pilot.

PROGRESSION CRITERIA: A year after randomising the first PDU/JSWT, we will assess the feasibility of the trial with the following progression criteria: 12 PDU/JSWT randomised (>9 modifications needed, \leq 8 stop trial); letters of support received from the remaining 24 PDU/JSWT (>19 modifications needed, \leq 18 stop trial); 168 participants enrolled (>123 modifications needed, \leq 122 stop trial); 80% followed-up at 4

months and 80% intervention adherence (>65% modifications needed, ≤ 64% stop trial). If all criteria are met, we will ask the Trial Steering Committee (TSC) to recommend progression to the trial.

Progression Criteria	Go	Revise strategy	Stop Trial
PDU/ JSWT randomised	≥12	9 to 11	≤ 8
PDU/ JSWT letters of support	≥ 24	19 to 23	≤ 18
Offenders enrolled	≥168	123 to 167	≤ 122
Adherence to the programme by offenders	≥ 80%	65 to 79%	≤ 64%
Follow up of offenders	≥ 80%	65 to 79%	≤ 64%

STOPPING CRITERIA: The trial may be prematurely discontinued by the Sponsor or CI on the basis of new safety information (e.g. that the ADVANCE-D Programme caused harm or greater risk) or for other reasons given by the Data Monitoring Committee (DMC) regulatory authority or ethics committee concerned. The trial may also be prematurely discontinued due to lack of recruitment or upon advice from the Trial Steering Committee (TSC), who will advise on whether to continue or discontinue the study and make a recommendation to the sponsor. If the study is prematurely discontinued, active participants will be informed, and no further participant data will be collected.

The DMC will provide advice to the TSC, who will advise the Sponsor in making the final decision on continuing or stopping the trial.

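### Section 3.10 records a man as not having completed ADVANCE-D because his tablet was not returned, whatever sessions he attended

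*Protocol*

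**What the plan says.** Protocol section 3.10, under digital poverty and literacy, gives two points at which a tablet is asked for. The general one is: "Participants will be asked to return their tablet to probation /JSW at the end of the study". The earlier one is: "If men do not attend any sessions each month (group or website), researchers will ask men to return the tablet". Men may use their own technology instead and have their data costs reimbursed. Men who are arrested or returned to custody are asked to arrange the return through someone else.

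The consequence of non-return follows: "If the device is not returned, it will be remotely wiped as far as is possible", and the team will also "remove website access for the participant and record their details as having been offered ADVANCE-D and not completed, for research and operational purposes". The section adds that lost, stolen and broken devices will be tracked as a rate. It does not say whether a device reported lost counts as not returned.

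Elsewhere, exposure is recorded by attendance. Section 3.7.10 defines dose received through counts such as the "number of sessions attended in group intervention", and records sessions offered separately. Section 4.1.1 records the reason when a man stops attending. The economic evaluation in section 10.7 shares out cluster costs by attendance. Sections 4.1.1, 10.4.3 and 10.10 leave adherence and compliance to the SAP. Section 10.4.1 states: "A CACE will be developed as a sensitivity analysis to the primary analysis".

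**The concern.** Returning a piece of equipment does not measure exposure to a programme. The protocol nevertheless makes an equipment event the trigger for a research record of non-completion, and gives no other rule for when a man is recorded as not having completed. The deferral to the SAP does not remove this, because the coding instruction is in the protocol and any completion or compliance variable built on it would inherit the error.

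The error need not be random. Custody is the circumstance section 3.10 itself links to difficulty in returning a device, and section 10 names return to prison as an intercurrent event. A man who finished the programme and was later imprisoned could therefore be mislabelled for a reason related to outcome.

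**Working it through.** The plan has no figure of its own to reproduce here. The check is a comparison of sections, followed by one conditional calculation.

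**Step 1: can the rule reach a man who finished?** Section 3.4.8 gives a 14-week programme with a booster one month after the last group session. Table 3 places the booster at week 20. Section 3.10 makes tablets due at the end of the study, and follow-up interviews run to 12 months after baseline (section 3.4.2). The general return point therefore falls after the programme is over, and a man can finish every session before the rule applies to him.

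**Step 2: same attendance, different records.** Take three men who each attended every session.

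| Man | Device | Attendance record (3.7.10) | Effect of the non-return rule (3.10) |
|---|---|---|---|
| A | Trial tablet, kept | Full | Recorded as not completed |
| B | Trial tablet, returned | Full | Rule not triggered |
| C | Own device | Full | Rule cannot apply |

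Man A's research record contradicts his own attendance record. The three differ only in what happened to a tablet.

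**Step 3: what does the label overwrite?** Nothing that can be found. Sessions offered, sessions attended, the reason for stopping and the cost allocation are each recorded on their own terms. The primary analysis in section 10.4.1 is by ITT on men followed up at 4 or 12 months and does not use completion.

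**Step 4: size, if the label were used as compliance.** Assumptions:

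- The CACE is the simple ratio for a binary complier.
- No control man receives ADVANCE-D.
- The label is the compliance variable, which no section states.

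Let p be true compliance and r the share of true completers who do not return the tablet.

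- Recorded compliance = p(1-r).
- CACE with correct coding = ITT/p.
- CACE with the label = ITT/[p(1-r)].
- Ratio of the two = 1/(1-r), which does not depend on p.

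The protocol does not give r, so a range is assumed:

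| r | 1/(1-r) |
|---|---|
| 5% | 1/0.95 = 1.05 |
| 15% | 1/0.85 = 1.18 |
| 30% | 1/0.70 = 1.43 |

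Men who received the programme but were coded as non-compliers would also breach the exclusion restriction on which a CACE relies. If compliance comes from session records, the factor is 1.00 whatever r is.

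**The case against.** The strongest reply is that the label may never be used. No section connects it to the CACE, to the dose data or to the progression criterion, and the definitions of adherence and compliance are left to an SAP that is not shown. The data for a correct variable are already being collected. That stands, and it is why the bias above is conditional.

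A second reply is that the sentence is meant for men who disengage and keep the tablet. It follows directly on the text about arrest and custody, and removing website access matters mainly for a man still in the programme. This is a plausible intention, but it is not what is written: the paragraph concerns every participant's duty to return the device. Even on this reading, a man who finished and was later imprisoned would be mislabelled.

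A reader might go further and infer any of the following. The protocol does not support them.

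- **That the recorded dose is wrong.** Session counts are kept separately, and the label is a status, not a count.
- **That returning the tablet makes a man a completer.** No section says so.
- **That the pilot would move from Go to Revise or Stop on its adherence criterion, "80% intervention adherence (>65% modifications needed, ≤ 64% stop trial".** Nothing ties the label to that criterion. Progression is also assessed a year after the first unit is randomised, whereas the general return point is the end of the study. The earlier requests, after a month without sessions or on arrest, would mainly reach men who really have stopped. Read literally, the monthly request could also reach a man after his booster, so an early false label is possible, but this does not establish an effect on the decision.

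**Conclusion.** The point holds as a wrong coding rule with limited reach. As written, section 3.10 produces a false research record of non-completion for any man who finished the programme and did not return a trial tablet, and this conflicts with the attendance-based record in section 3.7.10. A completion rate reported from that record would be too low, by an amount the protocol does not allow one to calculate.

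The primary ITT result, the session counts and the attendance-based costs are unaffected. A bias in adherence or in the CACE follows only if the SAP adopts the label. The factors of 1.05 to 1.43 rest on that condition and on assumed values of r from 5% to 30%. The CACE is in any case a sensitivity analysis.

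**What to change.** In section 3.10, delete from the non-return rule the instruction to record the man as not having completed for research. Wiping the device and removing website access can stay. Add one sentence saying that completion, adherence and CACE compliance are derived only from session attendance records, and that device non-return is logged as a separate equipment variable that never changes them. The sentence should name group, website and coaching sessions, because the dose-received text in section 3.7.10 does not spell out the last two. The SAP should use the same source.

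The cost is one sentence in the protocol. Attendance is already recorded, the monthly check in section 3.10 already requires group and website attendance to be known, and lost devices are already tracked.

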4.1 Intervention and comparator description

Regardless of allocation, all participants will have a supervising officer to manage risk and enforce the order/license. The supervising officer will oversee progress of the order to support them in successfully completing the requirements they are subject to.

4.1.1 **ACTIVE**

Intervention

[figure not shown]
ADVANCE-D proposes that behaviour change is facilitated by increasing understanding of the function of abusive behaviours and the contribution made by substance misuse and gendered attitudes. 46 It highlights individual risks for IPV including substance misuse, poor emotional regulation, and poor stress-coping. It teaches men how to reduce these risks by promoting self-regulation and personal goal setting. ADVANCE-D is a 33-session (14-week) programme (+ refresher session 4 weeks later) delivered in-person, remotely or hybrid. It includes: a 1:1 goal-setting session; a welcome to group preparation session; 6 group sessions [these are the 8 core sessions]; 12 self-directed website sessions with a digital coach (avatar) to recap and practise skills learned in the group each followed by 1:1 coaching sessions with a facilitator (12 weekly coaching sessions in total). It is delivered by 2 facilitators (ideally one female), trained in supervising PP/JSW. To manage risk, 4 case management meetings are scheduled with the ISS. Men offered ADVANCE-D can receive concomitant support for substance misuse.

Website sessions (n=12)

- 1: Introduction
- 2: Managing myself
- 3: Being a man
- 4: Impact on her
- 5: Children and parenting
- 6: Relating
- 7: Improving communication
- 8: Dealing with distress
- 9: Planning to be better
- 10: Positive relationships
- 11: New futures
- 12: Recap 'what have we learned?

Group sessions (n=6)

- 1: Understanding abuse
- 2: Handling challenges
- 3: Difficulties in families
- 4: Times of distress
- 5: Relating well
- 6: Doing it differently

Supervising Officers would also be expected to see the ADVANCE-D participants face-to-face in addition to the structured intervention to meet national standards.

To give an example of a fortnight in the programme, the diagram below illustrates that there is an online group delivered every fortnight; in the two weeks following each group, participants complete two practice website sessions each followed by a coaching call. Participants advise the facilitator when they were intending to complete the session so that the coaching call is booked in to follow. The 12 weekly self-directed website sessions are guided by a digital coach (avatar) to recap and practice skills learned in the online group sessions. The online coach verbalises the content and the text also appears on screen, so participants have the option to listen to the coach and/or read the text. Coaching calls are delivered by a facilitator to go over the materials in the previous group and website session, check in with the participant around their relationship and substance use, especially any change in risk, and continue to enhance motivation and revisit goals. A refresher session is offered one month after the last online group takes place.

The online content is managed by Maudsley Learning. As an NHS Trust, Maudsley Learning hosts digital products and services within Microsoft Azure Cloud Services. Specifically, the ADVANCE-D intervention online will be hosted on a Virtual Machine within Azure using resource groups within the stack, managing user accounts with Azure Active Directory B2C, and working within Azure security policies. Maudsley Learning work with a Microsoft Gold Certified Partner for management of the cloud architecture, applications and Active Directory within the stack. The Microsoft Azure Data centre region is UK South (location London). Maudsley Learning work to the following compliance guidance, standards and policies:

- ➤ Government Cloud Security Guidance
- > NHS Digital Standards for web products
- South London and Maudsley NHS Foundation Trust. Personal information and data protection policy
- ➤ South London and Maudsley NHS Foundation Trust. Privacy policy

Adherence

If a participant stops attending the ADVANCE-D Programme the reason for this will be recorded e.g. 1) participant reason given; 2) violation of condition. Should a participant withdraw from the ADVANCE-D Programme, efforts will be made to continue to obtain follow-up data, with the permission of the participant. Men in both treatment arms will have a supervising PP/ JSW to monitor compliance to the community sentences. Any violation of conditions will be referred back to court. If participants are finding it hard to attend scheduled sessions, then a meeting between their facilitator, PP/ JSW and a member of the ADVANCE-D research team will develop a strategy to address this issue. Options will range from offering specific 1-1 input to catch the participant up; linking with a buddy to help attendance, devising personalised reminders e.g. texts to remind participants of day and time of attendance or personalised support, help to log on via phone, to address barriers for engagement or additional motivational input to minimise ambivalence or 1-1 to enhance understanding. Where participants appear unable to attend despite bespoke support, they will be considered for alternative input, including different content or different delivery mode. As ADVANCE-D will not be specified on the order but fall within the requirement to undertake offence-focussed work, there is no need to return to court to vary the order if men decline to participate.

Adherences will be reported as per the Statistical Analysis Plan.

Integrity Support

Receiving supervision from other staff when delivering IPV perpetrator programmes has been shown to reduce IPV recidivism.³⁵ Fortnightly online integrity support meetings for ADVANCE-D facilitators will be led by clinical lead and co-CI [name] (Chartered Forensic Psychologist) and to discuss delivery issues and address any expected problems with the next two sessions. These integrity support meetings will check intervention fidelity, cover the core material to be delivered in the forthcoming sessions and review any issues that have arisen when delivering previous sessions to promote fidelity to the model and reduce likely non-adherence. Any deviation from delivery as planned will be noted and included as a factor in the evaluation of acceptability and feasibility. Separate online fortnightly integrity support meetings for ISS workers will be led by [name], CEO of Welsh Women's Aid to support ISS to respond to any issues raised when supporting women. A register of attendance will be kept.

Fidelity

All online group sessions will be recorded within Microsoft Teams with participants' and facilitators' consent. Researchers will check a random sample of 10% of the recording intervention fidelity, using a predefined checklist for each group session. Recordings of the integrity management meetings will contribute to understanding fidelity.

